### **8.7 Measurement of insulin secretory response to meal challenge:**

Mixed meal tests have been proposed to have similar sensitivity and reproducibility to oral glucose tolerance testing (OGTT) for the detection of hyperglycemia and diagnosis of glucose intolerance (47,48) and we have substantial experience in performing these tests in older subjects. Indeed, a standard mixed meal challenge, rather than an oral glucose challenge, represents a more physiologically relevant stimulus in that it may more closely mimic the metabolic changes experienced by individuals in daily life, and is better tolerated than an OGTT. It also represents a more integrated measure of nutrient metabolism than intravenous challenge tests, since it includes the contribution of the incretin hormones.

We will study subjects following an overnight fast and after a test meal of 100 g CHO, 20 g protein, and 20 g fat. Blood sampling will be performed through an indwelling intravenous catheter, fasting and 15, 30, 45, 60, 90, 120 and 180 minutes following the meal, for measurement of glucose, insulin, C-peptide and glucagon levels. Plasma triglycerides and FFA levels will be measured fasting and at 60, 120 and 180 minutes. Subjects will be provided with a standard meal and snack to consume at home the night prior to the MMT and will fast after 10 pm, in order to minimize metabolic variability between tests. Glucose and insulin levels will be used to calculate the area under the curve (AUC) using the trapezoidal method.

Glucose-stimulated insulin secretion can be assessed using a variety of techniques, including hyperglycemic “clamp” studies and the frequently sampled intravenous glucose

tolerance test. However, these procedures could be considered to be less physiologic, as they do not capture the contribution of incretin hormones, and may be more burdensome for older subjects. Standard mixed-meal tests with frequent blood sampling and application of mathematical modeling have been used to evaluate insulin secretion, and have been reported to produce results comparable to more invasive and less physiologic tests (49,50).

In collaboration with our colleague, [name], indices of  $\beta$ -cell function will be estimated from plasma glucose and C-peptide concentrations using the *oral minimal model of C-peptide secretion*, with kinetics calculated from deconvolution of plasma C-peptide concentrations measured during the standard mixed meal (51) and using parameters for C-peptide kinetics and volume of distribution as measured by Van Cauter et al (52). Insulin secretory dynamics can be broken down into dynamic and static components of  $\beta$ -cell responsivity to glucose. The dynamic responsivity index, termed  $\Psi_{\text{dynamic}}$ , measures the  $\beta$ -cell secretory response to the rate of change of glucose concentration. This measure approximates the first phase of insulin release and defines the response to a given increment in glucose. Conversely, the static responsivity index ( $\Psi_{\text{static}}$ ) measures the beta cell secretory response to a given glucose concentration. This static measure is believed to represent the provision of new insulin into the secretory pool. The two Phi factors can be combined into a  $\Psi_{\text{total}}$ . The appropriateness of the insulin secretion for the prevailing degree of insulin resistance will be determined by the disposition index (DI) calculated as the  $\Psi_{\text{dynamic}}$ ,  $\Psi_{\text{static}}$  and  $\Psi_{\text{total}}$  times the insulin sensitivity (53), which will be determined by the method of Matsuda Error! Bookmark not defined., allowing calculation of a DI for subjects who do not undergo the euglycemic clamp.

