##### 1.2 BACKGROUND AND SIGNIFICANCE:

###### 1.2. Significance of Diabetes in Indian population and South Asians living in the United States:

Diabetes is rapidly becoming a global epidemic. India has the world's highest prevalence of diabetes, expected to rise to 80 million by 2030 (1). As a consequence of rapid Westernization, many Indians are developing type 2 diabetes (T2DM). Of note, T2DM incidence in Indians rises sharply when body mass index (BMI) rises above 22 kg/m^2 (2).

Additionally, the diabetes population in India and other LMICs includes many patients with low BMI and severe complications of diabetes. Various reports suggest that these patients are surprisingly insulin resistant considering their lean body habitus. Some of these individuals have Fibrocalculous Pancreatic Diabetes (FCPD), in whom pancreatic calculi and/or ductal dilatation may contribute to the etiology of their disease (3). Many, however, are classified as **Lean Diabetes**, identified clinically by early onset, high insulin requirements, absence of pancreatic calculi or ductal dilation, and low BMI (typically  $\leq 17\text{kg/m}^2$  at presentation). The majority of young adults with diabetes in India are likely to have FCPD or lean diabetes (3). Both conditions differ from type 1 diabetes by persistent C-peptide response to nutrient stimuli, and absence of ketosis and pancreatic beta cell autoimmunity markers (4). Lean diabetes tends to present in young adults between the ages of 20 and 40 and afflicts men and women at a 2:1 ratio. Despite its sizeable prevalence, lean diabetes remains a relatively unknown disease that stirs conflicting opinions regarding its classification, diagnostic criteria, and pathogenesis (5). Of note, patients with lean diabetes appear to have elevated VLDL and triglycerides as well as insulin resistance based on insulin tolerance tests (6).

It has increasingly become apparent that marked ethnic variability in the clinical features of diabetes exists. Variability in the prevalence and pattern of disease among ethnic groups

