### **1.3 SIGNIFICANCE:**

It is highly intriguing, in the twenty-first century, to encounter a condition as prevalent as lean diabetes yet about which so much remains to be learned. The diabetes literature is dominated by studies conducted in high income countries, where this condition is never encountered. *These would be the first truly comprehensive studies defining the body composition and metabolic features of lean diabetes.* Scientifically, this application will explore a novel frontier in the intriguing dynamic between fat metabolism and insulin sensitivity.

**Clinical relevance:** Given India's high prevalence of diabetes, of which a substantial yet poorly defined proportion is likely to have lean diabetes, this proposal would have considerable clinical relevance for India and many other countries. In the absence of

sufficient information about this condition and its management, many lean diabetes patients are labeled as type 1 diabetes and are prescribed insulin. Unfortunately, inconsistent food availability among poor patients results in many insulin-induced hypoglycemic deaths. A better understanding of the metabolic defects of this condition should be very helpful in pointing towards more appropriate therapeutic approaches. Specifically, being able to clearly demonstrate that these subjects are insulin resistant would favor the use of safer, cheaper oral insulin sensitizing agents. This application therefore seeks to shift current clinical practice paradigms for underweight patients with diabetes, by studying a novel hypothesis concerning the pathophysiology of lean diabetes. *Defining the metabolic defects of lean diabetes could therefore have tremendous therapeutic benefit for millions of patients with this elusive condition.*

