**This is an observational study and hence there will be no randomization.**

**Schedule of proposed clinical studies:**

**TIMELINE:**

|  | Year 1 | Year 2 | Year 3 |
|--|---------------|---------------|---------------|
| Recruitment efforts and screening visits | 50            | 30            | 20            |
| Body composition analysis                | 10            | 25            | 25            |
| Clamp studies                            | 10            | 25            | 25            |
| Data analysis                            | X             | XX            | XX            |
| Manuscript preparation & presentations   |               | X             | XX            |

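### The meal-test AUC in section 8.7 uses insulin rather than C-peptide, so it may count injected insulin as secretion; the disposition index is exposed only through its Matsuda factor

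*Combined protocol and SAP*

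**What the plan says.** Section 8.7, which section 4.3 largely repeats, describes the mixed-meal test for Objective 3. Samples are taken "fasting and 15, 30, 45, 60, 90, 120 and 180 minutes following the meal, for measurement of glucose, insulin, C-peptide and glucagon levels". The AUC sentence then names two analytes only: "Glucose and insulin levels will be used to calculate the area under the curve (AUC) using the trapezoidal method".

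The same section goes on to model-based measures. The dynamic, static and total responsivity indices "will be estimated from plasma glucose and C-peptide concentrations using the" oral minimal model. The disposition index is each of these "times the insulin sensitivity (53), which will be determined by the method of Matsuda". The stated advantage is coverage, "allowing calculation of a DI for subjects who do not undergo the euglycemic clamp".

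On insulin treatment, section 1.2 describes lean diabetes as "identified clinically by early onset, high insulin requirements", and section 1.3 says "many lean diabetes patients are labeled as type 1 diabetes and are prescribed insulin". Section 5.0 lists a T1DM group of 20 and requires nondiabetic subjects to be on no medication. Section 6.2 does not name insulin use as an exclusion. Insulin handling before a test is described in section 3.2 for the clamp; for the meal test, section 8.7 gives only a standard evening meal and an overnight fast.

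**The concern.** Injected insulin is measured in plasma but carries no C-peptide. Section 8.5 specifies radioimmunoassay and does not say that it separates injected from endogenous insulin; free insulin is listed only among the clamp measurements in section 4.2. In a subject treated with insulin, the insulin AUC can therefore be a sum of what was secreted and what was injected. Treatment is likely to go with group, since controls have none, so the excess would not average out in a between-group comparison.

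Objective 3 asks how much insulin these patients secrete, and section 1.3 hopes the answer will inform therapy. An AUC inflated by treatment could make secretion in lean diabetes look closer to normal than it is. The hormone that avoids this problem is sampled in the same draws but is not summarised as an AUC.

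**Working it through.** The plan gives no figure for the meal test. Its one sample-size figure, 20 per group for clamp glucose uptake, is roughly reproduced. With a difference of 10.2 - 8.0 = 2.2, SD sqrt((2.0² + 2.5²)/2) = 2.264 and two-sided alpha 0.05 (assumed), the exact t calculation needs 18 per group for 80% power, and 20 gives 0.85. Nothing below changes it.

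**Which measures contain insulin**

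- Insulin AUC: measured insulin only.
- Responsivity indices: glucose and C-peptide, so injected insulin does not enter directly. It can still act indirectly, by lowering glucose or suppressing secretion.
- Disposition index: responsivity (C-peptide) × Matsuda sensitivity (glucose and insulin). Only the second factor is exposed.

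**Formulas.** The Matsuda formula is not printed in the documents. I assume the standard form, 10000 / sqrt(G0 × I0 × Gmean × Imean), where G0 and I0 are fasting values. Let injected insulin multiply both fasting and mean insulin by k, and let glucose be multiplied by g at both points. Then, with responsivity unchanged:

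- total insulin AUC is multiplied by k;
- Matsuda, and so the disposition index, is multiplied by 1 / (k × g).

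**Values.** The documents give no injected fraction, so k = 1.25 to 2.00 is an assumed range, and g = 0.80 is illustrative.

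| k | Insulin AUC | Disposition index, g = 1 | Disposition index, g = 0.80 | g at which it is unchanged |
|---|---|---|---|---|
| 1.25 | × 1.25 | × 0.80 | × 1.00 | 0.80 |
| 1.50 | × 1.50 | × 0.67 | × 0.83 | 0.67 |
| 2.00 | × 2.00 | × 0.50 | × 0.63 | 0.50 |

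If the addition is uneven, say 50% at fasting and 25% on average with glucose fixed, insulin AUC is × 1.25 and Matsuda is × 1/sqrt(1.50 × 1.25) = 0.73.

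The AUC column takes the total area, because section 8.7 does not say that the fasting value is subtracted. A constant injected background of c would add 180c to the total area over 180 minutes and nothing to an area above fasting.

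**Clamp coverage.** The "Clamp studies" row of the timeline gives 10 + 25 + 25 = 60. Section 5.0 plans 4 × 20 = 80 subjects. If each clamp is a different subject, 20 subjects have none. The three groups named in section 9 would total 3 × 20 = 60, but the documents do not say which subjects are clamped.

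**The case against.** The strongest reply is that secretion is already measured from C-peptide. The responsivity indices address Objective 3 directly, and the AUC sentence does not call insulin AUC the measure of secretion. This stands in part: it confines the problem to one summary and one factor of another. It does not explain why the only AUCs named in a section on secretory response leave out C-peptide.

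Second, insulin use among enrolled subjects is inferred. Sections 1.2 and 1.3 describe patients in general. Subjects must show a C-peptide response, and section 9 does not include the T1DM group in its comparison. Section 6.2 also excludes chronic illness needing medication. Read literally, that would bar all treated diabetes, so it is presumably meant for other conditions. The premise is therefore likely but not established, and the size of the effect is unknown.

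Third, a reader might infer that the disposition index is invalid in treated subjects, or that it drops by 20% to 50% with no physiological change. The documents do not support either reading. Its secretion factor is C-peptide based. Injected insulin is active and lowers glucose, which sits in the same denominator, so 20% to 50% describes the case of no glucose response. For sensitivity, total circulating insulin is also the relevant exposure, so counting injected insulin there is not the same error as counting it as secretion.

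Fourth, a reader might conclude that clamp sensitivity should replace Matsuda. That is a trade-off, not a correction. Section 3.2 infuses insulin overnight in both DM groups to remove glucose-induced resistance before the clamp, whereas section 8.7 wants secretion judged against the resistance that prevails. Clamp sensitivity paired with meal-day secretion could shift the index between groups in its own way, and unclamped subjects would have no value. This objection stands in full.

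**Conclusion.** The point holds for the AUC. Insulin AUC may mix injected with secreted hormone, to a degree that differs by group, while C-peptide from the same draws is not summarised. The overstatement equals the injected share: 25% to 100% over the assumed range, for a total area. It rests on two inferences, namely that some enrolled diabetes subjects use insulin and that injected insulin is present at the meal test. The documents make the first likely and are silent on the second.

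For the disposition index the point is narrower. Only the Matsuda factor is exposed, and the fall of 20% to 50% requires the standard formula, the assumed insulin range and unchanged glucose. With a fall in glucose the effect shrinks, and it vanishes when glucose falls to 1/k of its value. The responsivity indices are not directly contaminated.

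Meal-test measures are not among the examples of primary measures in section 9, and no sample size or power figure changes. This is a free improvement.

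**What to change.** In sections 8.7 and 4.3:

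- Name C-peptide AUC over 0-180 minutes, by the same trapezoidal rule, as the AUC measure of secretion, and say whether it is total or above fasting.
- Keep insulin AUC, described as circulating insulin and not as secretion.
- Keep the Matsuda disposition index for all subjects, and report it also by insulin-treatment status. With about 20 per group this split is descriptive.
- Add a disposition index using clamp sensitivity in clamped subjects, labelled supplementary. Note beside it that clamp sensitivity is measured after overnight insulin in the DM groups.
- Report insulin treatment by group, and state how it is handled around the meal test. What that handling should be is a clinical matter, and none is proposed here.

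The cost is wording and a few extra table rows. C-peptide is already sampled, and concomitant medication is already recorded at screening (section 7.1). The only possible new data item is the timing of the last insulin dose before the meal test. The supplementary index will be missing for anyone without a clamp.

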## 8.8 Fat Biopsies and Analysis:

**Biopsies:** Participants will have fat biopsies performed in the perumbilical region approximately one month following the clamp study. A small ~1-2 cm cutaneous incision will be performed under local anaesthesia (Lidocaine 1%) and 1-2 g of adipose tissue will be obtained by open biopsy technique.

Initially, the fat biopsies were planned to be obtained by aspiration technique. However, given the low BMI of the lean diabetic subjects, an aspiration biopsy is likely to be very difficult. We would therefore like to perform an open subcutaneous abdominal fat biopsy in each study participant. Moreover, given the complex nature of the clamp study we propose to perform the fat biopsy on a separate date approximately one month following the clamp study.

**Adipose tissue specimens-** Whole adipose tissue for analysis by rt-PCR will be immediately homogenized in Trizol (Life Technologies, Bethesda, MD) with a Tissumizer homogenizer. Remaining fresh adipose biopsy specimens will be immediately digested with collagenase type 1. Adipocytes will be subsequently separated from stromal cells by centrifugation and filtration. Macrophages will be separated from stromal cells by CD14+ specific antibody coated beads. Subsequent mRNA extraction and analysis of gene expression by real-time QPCR of each adipose tissue fraction will be performed .

We will quantify adipose tissue macrophages with **immunohistochemistry**. To measure macrophage content in adipose tissue by immunohistochemistry, samples will be fixed and embedded in paraffin (54). For **immunofluorescence**, tissue sections will be stained with primary antibodies to human CD68 and PAI-1 followed by fluorescent secondary antibodies, and images quantified.

**FACS analysis:** After digestion with collagenase, the pellet of stromal cells will be treated with red blood cell lysing buffer followed by incubation with saturating amounts of FITC-labeled human CD14+ or CD163+ antibody, then washed and analyzed immediately by using a FACScalibur flow cytometer (Becton Dickinson, San Jose, CA). **Intracellular cytokine staining** will involve a modification of basic flow cytometry that will be used for the simultaneous analysis of surface molecules and intracellular antigens at the single-cell level. Cells will be stained for surface antigens, then fixed to stabilize the cell membrane, and then permeabilized with the detergent saponin to allow anti-cytokine antibodies to stain intracellularly.

## 9. STATISTICAL ANALYSIS

**Analysis of Variance (ANOVA):** A one-way ANOVA will be used to compare the primary measures (eg. glucose uptake, glucose production, IHTG) among the three study groups. When the ANOVA indicates a significant difference, unpaired t-tests will be performed to distinguish which groups differ. The null hypothesis is that the primary measures will not differ between the three groups: the nondiabetic, lean diabetes and T2DM groups. These analyses will be performed in collaboration with Einstein's biostatistician .

## POWER ANALYSIS

It should be emphasized that the proposed comparisons represent 'ground-breaking' studies, as such measures have not yet been performed in individuals with lean diabetes. Based on our hypotheses, we predict that both DM groups will have similarly reduced rates of insulin-stimulated glucose uptake, while glucose uptake in the lean diabetes group will differ from matched nondiabetic controls to a similar extent as the difference observed between obese and lean subjects in our preliminary data. A sample size calculation was therefore performed based on an unpaired two-tailed t-test of between-group difference. Sample size analyses were performed, using NCSS/Pass software, to calculate the minimum sample size needed to achieve at least 80% power to detect a statistically significant difference in the primary outcomes of interest. Using our preliminary data in which mean glucose uptake was 8.0 mg/kg.min with SD of 2.0 mg/kg.min in the obese group, vs. mean glucose uptake of 10.2 mg/kg.min with SD of 2.5 mg/kg.min in the lean group, this calculation yielded a sample size of 20 per group.

## Potential Risks:

Potential risks to the subjects include the following:

1. Blood withdrawal: The total amount of blood sampled will not exceed 190 ml per study, less than half of that donated by a blood donor.
2. 20% dextrose: The infusion of 20% dextrose may be associated with local venous irritation. This will be minimized by use of a large-bore antecubital vein in which the glucose will be infused.
3. D2G: is a non-radioactive glucose tracer and is not associated with any known side effects at the doses used.
4. Glucagon infusion in high doses can cause gastrointestinal symptoms such as cramps and nausea, and produce hyperglycemia in persons with glucose intolerance. The doses to be employed here are intended to maintain plasma glucagon at basal levels.

5. Growth Hormone: At higher doses and for prolonged periods of exposure, growth hormone (rhGH) has either insulin-like or insulin-antagonistic effects on carbohydrate and lipid metabolism, however the proposed infusion is for physiological replacement during SRIF infusion and is unlikely to have adverse effects.
6. Hypoglycemia: is unlikely to develop in these subjects because of the desired plasma glucose targets (90 mg/dl during the normoglycemic studies), the low rates of insulin infusion, and the constant blood glucose monitoring.
7. Somatostatin: At the proposed physiological replacement doses has no known side effects.
8. Ocreotide: At the proposed physiological replacement doses has no known side effects.

### **Protection Against Risks:**

#### Recruitment and Informed Consent Procedures:

Consent will be initially obtained during telephone screening performed by a research fellow or the study coordinator. Formal consent procedures which adhere to the Committee on Clinical Investigations of the Albert Einstein College of Medicine will be followed. Specifically, each subject will be verbally informed in layman's language of the purpose, benefits and possible risks of the studies. They will then read the written consent form in the presence of a member of the research team and a physician who will answer any further questions. The subject and witness shall be asked to sign the consent form which will be kept in the patient's chart. Each subject's potential participation in related experiments (for example, when each subject is asked to perform repeat studies) will be explicitly stated.

All clinical data on the subjects will be confidential. Data generated in these studies will be considered only relevant for research purposes and will not be included in any clinical databases or the patient's chart. Since the GCRC databases are coded, the study data will not be available on any clinical database system.

Procedures employed to protect subjects from undue risks include the following:

- 1) Blood withdrawal: Blood withdrawal during any single study will be limited to less than 190cc and subsequent studies will be separated by at least, a four week interval. The infusion and withdrawal catheters may produce infection or local hematoma, but strict aseptic technique will be observed by the experienced physician performing the procedure.
- 2) 20% glucose: Vein irritation with 20% glucose infusion will be prevented by use of a large-bore antecubital vein.
- 3) Glucagon: Symptoms of mild nausea will be treated with antiemetic medications, if needed.
- 4) Hypoglycemia: All of these studies will be performed by a physician, hypoglycemia will be prevented by blood glucose sampling every 5-10 minutes and if inadvertent hypoglycemia develops can be rapidly treated by glucose infusion.

